9.2 Storage of Study Equipment or Related apparatus

There is no specific equipment used for this study. The spirometer and FeNO analysers are not study equipment (they are part of recommended routine care) and will be stored in locked University of Leicester or participating GP premises when not in use.

9.3 Compliance with Study Treatment

There are no compliance issues with this study plan

10. SAFETY REPORTING

10.1 Definitions

10.1.1 Adverse Event (AE)

An AE or adverse experience is:

Any untoward medical occurrence in a patient or clinical investigation participants, which does not necessarily have to have a causal relationship with this treatment.

An AE can therefore be any unfavourable and unintended sign (including an abnormal laboratory finding), symptom or disease temporally associated with the the study, whether or not considered related to the study.

10.1.2 Adverse Reaction (AR)

All untoward and unintended responses related to the study.

All cases judged by either the reporting medically qualified professional or the sponsor as having a reasonable suspected causal relationship to the study qualify as adverse reactions.

10.1.3 Severe Adverse Events

To ensure no confusion or misunderstanding of the difference between the terms "serious" and "severe", which are not synonymous, the following note of clarification is provided:

The term "severe" is often used to describe the intensity (severity) of a specific event (as in mild, moderate, or severe myocardial infarction); the event itself, however, may be of relatively minor medical significance (such as severe headache). This is not the same as "serious," which is based on patient/event outcome or action criteria usually associated with events that pose a threat to a participant's life or functioning. Seriousness (not severity) serves as a guide for defining regulatory reporting obligations.

10.1.4 Serious Adverse Event or Serious Adverse Reaction

A serious adverse event or reaction is any untoward medical occurrence that at any dose:

- Results in death,
- Is life-threatening,

NOTE: The term "life-threatening" in the definition of "serious" refers to an event in which the participant was at risk of death at the time of the event; it does not refer to an event which hypothetically might have caused death if it were more severe.

- Requires inpatient hospitalisation or prolongation of existing hospitalisation,
- Results in persistent or significant disability/incapacity, or
- Is a congenital anomaly/birth defect.
- Other important medical events*

*Other events that may not result in death, are not life threatening, or do not require hospitalisation, may be considered a serious adverse event when, based upon appropriate medical judgement, the event may jeopardise the patient and may require medical or surgical intervention to prevent one of the outcomes listed above.

10.1.5 Expected Serious Adverse Events/Reactions

There are no active interventions involved with this study. As such we do not expect any adverse events directly related to the study.

10.1.6 Suspected Unexpected Serious Adverse Reactions

A serious adverse reaction, the nature or severity of which is not consistent with the applicable product information.

10.2 Reporting Procedures for All Adverse Events

All AEs occurring during the study observed by the investigator or reported by the participant, whether or not attributed to study, will be recorded on the CRF.

The following information will be recorded: description, date of onset and end date, severity, assessment of relatedness to study, other suspect device and action taken. Follow-up information should be provided as necessary.

AEs considered related to the study as judged by a medically qualified investigator or the sponsor will be followed until resolution or the event is considered stable. All related AEs that result in a participant's withdrawal from the study or are present at the end of the study, should be followed up until a satisfactory resolution occurs.

It will be left to the investigator's clinical judgment whether or not an AE is of sufficient severity to require the participant's removal from treatment (see section 7.7). A participant may also voluntarily withdraw from treatment due to what he or she perceives as an intolerable AE. If either of these occurs, the participant must undergo an end of study assessment and be given appropriate care under medical supervision until symptoms cease or the condition becomes stable.

The severity of events will be assessed on the following scale: 1 = mild, 2 = moderate, 3 = severe.

The relationship of AEs to the study will be assessed by a medically qualified investigator.

Note: Due to the nature of the study it is not the intention to be recording or reporting AEs or SAEs

10.3 Reporting Procedures for Serious Adverse Events

All SAEs, except those expected ones defined in section 10.1.5 that do not require immediate reporting (see 10.1.5), must be reported to the Sponsor within one working day of discovery or notification of the event. The Sponsor will perform an initial check of the information and ensure that it is reviewed at the next R&D Management meeting. All SAE information must be recorded on an SAE form and sent to the Sponsor using the appropriate reporting form and the contact details on there. Additional information received for a case (follow-up or corrections to the original case) needs to be detailed on a new SAE form which must be sent to the Sponsor using the appropriate reporting form and the contact details on there.

The Sponsor will report all SUSARs to the Research Ethics Committee concerned. Fatal or life-threatening SUSARs must be reported within 7 days and all other SUSARs within 15 days. The CI will inform all investigators concerned of relevant information about SUSARs that could adversely affect the safety of participants.

In addition to the expedited reporting above, the CI shall submit once a year throughout the study or on request an Annual Report to the Ethics Committee which lists all SAEs / SUSARs that have occurred during the preceeding 12 months.

Note: Due to the nature of the study it is not the intention to be recording or reporting AEs or SAEs

11. STATISTICS

11.1 Description of Statistical Methods

The qualitative data regarding opinions and barriers to implementation derived from change questionnaires conducted with the participating GP practices will be presented in report form. Appropriate non-parametric tests such as Kruskal-Wallis, Wilcoxon paired signed and Friedmans 2-Way ANOVA will be used to assess data; including the changes in number of children diagnosed with asthma, the number of misdiagnoses and alterations in prescribing (number of salbutamol inhalers/steroid courses) as a result of implementation of objective lung function tests. Paired t-tests or paired Wilcoxon signed rank tests will be used to assess the change in asthma control test scores, number of school days missed and number of carer work days missed.

A generalized linear mixed model with logit link function will also be used to compare the proportion of children with a personalised asthma plan and other secondary outcomes. The models will include important covariates such as age, gender and ethnicity, and the clustering effect of GP clinic will be accounted for. The effect of GP clinic will also be assessed by fitting a mixed effects model, GP clinic will be fitted as a random effect, covariates such as age, gender and ethnicity will be fitted as fixed effects.

All statistical analysis will be performed using R 3.2.0 (<http://www.r-project.org/>) and SPSS v22.

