4. BACKGROUND AND RATIONALE

In the UK the latest figures indicate that a total of 4.1 million people receive treatment for asthma (1). Of these approximately 1.1 million are children over the age of 5 years, which is the equivalent of one in ten children in the UK (2).

Despite the common nature of asthma there is no gold standard test available to diagnose the condition. The diagnosis is generally based on a thorough clinical history taken by an experienced clinician. Studies in adult populations however suggest that many are misdiagnosed including over and under-diagnosis of asthma (3-6). Over-diagnosis may affect up to 30% of adults diagnosed with asthma (3) and can result in inappropriate and unnecessary use of asthma medications and increased healthcare costs. Under-diagnosis often results in poor control and reduced quality of life.

Under-diagnosis and under-treatment of childhood asthma in primary care have been reported from several European countries (7-8) including the UK (9). The International Study of Asthma and Allergies in Childhood (ISAAC) for example reported that one-third of children aged 12 to 14 years in Great Britain with frequent night time wheezing had no diagnosis of asthma (9). Getting the diagnosis right in children is important because children have the highest asthma hospital admission rates for any age-group with asthma and under-diagnosis is associated with poor asthma control. Moreover, inappropriate treatment of children who do not have asthma with asthma medications can lead to unnecessary side-effects including a decreased growth velocity resulting from long-term inhaled corticosteroid use.

A recent draft NICE guideline (10) for asthma diagnosis and monitoring, originally due for publication in July 2015, recommends the use of objective tests including spirometry and FeNO testing to diagnose asthma in all patients 5 years and older under investigation for asthma. Recent BTS/SIGN asthma guidelines published in October 2014 also state that spirometry is superior to peak flow measurements, currently the most widely used lung function test in primary care in the management of asthma (11).

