5.2 Secondary Objectives

The secondary objectives relate to investigating the impact of implementing the new NICE guidelines on the processes and outcomes of childhood asthma care and will include:

1. The number of children in which a diagnosis of asthma can be confirmed using spirometry and FeNO testing
2. The number of misdiagnoses identified using lung function tests
3. The impact of implementation to health economics

[figure not shown]

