6. STUDY DESIGN SUMMARY

6.1 Summary of Trial Design

This study will employ both qualitative and quantitative measures in order to evaluate the resources required to implement routine lung function testing for children in primary care; and to investigate the impact this would have on diagnosis in children with suspected or presumed asthma. In total we hope to recruit between 3-6 GP sites across Leicestershire and Northamptonshire for the study, which would represent a patient population of ~120,000-150,000 people, representing 1500-2000 children potentially eligible to take part in the study based on our preliminary data. Primary care sites will be approached by the study team with assistance from the CCG R+D manager for Leicester ([name]) and the CRN locality manager for East Midlands ([name]). We aim to recruit sites of differing sizes and with different patient demographics.

Site survey questionnaires will be completed for each site by the study team to gather information about the individual practice's patient population and current asthma review set up. Readiness for change questionnaires will be used to investigate staff opinions, concerns and perceived barriers to implementation. These will be sent out to GPs, practice nurses, HCAs and practice managers at each participating site. The study team will develop and refine a package of training and support which will be based on an existing training programme for primary care practitioners to perform spirometry on adult patients with COPD in Leicestershire primary care practices. We will evaluate the success of the training by supporting and monitoring the primary care practitioners utilising these tests in primary care asthma review clinics. The length of training required in order for different staff groups to be able to perform spirometry and FeNO testing independently will be documented.

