We will assess additional capacity needs by timing how long each lung function test takes to perform in addition to the routine asthma review at each surgery. We will also be able to evaluate the number of patients who can be reliably reviewed and tested per session, thus elucidating how many sessions a typical GP practice would have to support in order to provide regular lung function testing to children. This information would further inform the costs required to sustain new NICE recommended practice.

Health Economic Analysis

This will take the form of a questionnaire delivered to parents at the time of the asthma review and a further postal questionnaire 3-6 months following the review. Analysis of this data will be supported by a health economist.

Assessment of Impact of Implementation to Processes of Care

Following the initial review appointment, we will access the electronic records of consented participants. We will seek information on changes to prescribed asthma medications (bronchodilators, oral steroids and inhaled steroids), exacerbations since review, hospital admissions/attendances since review and whether their originally diagnoses had changed as a result of the availability of objective tests.

With parental consent, we will also send out a repeat ACT by post 3-6 months following the initial review.

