11.2 The Number of Participants

We plan to recruit 1000 children into the study. This number has been derived from the expected number of children in the participating practices who would meet the inclusion criteria based on epidemiological data and preliminary searches. It also takes into consideration the capacity of the study team, the study length and anticipated recruitment rates of 50-70%.

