11.3 The Level of Statistical Significance

All statistical tests will be performed at the alpha=5% level.

11.4 Criteria for the Termination of the Trial.

Once we have accessed the records of the final child to be recruited and they have returned the follow up questionnaire.

11.5 Procedure for Accounting for Missing, Unused, and Spurious Data.

A table listing all key variables with percentage of missing data will be reported and where possible the reason for missing data will be reported. Within the multivariate regression framework missing data will be imputed using multiple imputation. To avoid bias, where it can be reasonably established that data is not missing at random, covariates will not be imputed, a complete case analysis will be used. Outcome variables missing not at random will not be imputed, sensitivity analysis will be performed and an assessment of the models made based on the missing at random assumption. Spurious data will be reported and where possible correct values will be inserted, if it is not possible to supply correct values, value will be deleted.

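### Section 11.1 assigns rank tests to two yes/no diagnosis outcomes: misdiagnosis has no pre-test value to pair, and net change in diagnoses cannot show removals and additions that cancel

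*Combined protocol and SAP*

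**What the plan says.** Section 11.1 states: "Appropriate non-parametric tests such as Kruskal-Wallis, Wilcoxon paired signed and Friedmans 2-Way ANOVA will be used to assess data". The outcomes it lists are "the changes in number of children diagnosed with asthma, the number of misdiagnoses and alterations in prescribing". The first two correspond to secondary objectives 1 and 2. Section 5.2 words the second as "The number of misdiagnoses identified using lung function tests".

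Section 11.1 does not pair tests with outcomes and does not say whether the unit is the child or the practice. It goes on to plan a logit mixed model, allowing for GP clinic, for the proportion of children with a personalised asthma plan and for further secondary outcomes that it does not name.

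Other relevant statements:
- Section 9.1: the records of consented children will be used to find "whether their originally diagnoses had changed as a result of the availability of objective tests".
- Section 4, citing studies in adults: "many are misdiagnosed including over and under-diagnosis of asthma". It then cites under-diagnosis in children.
- Section 6.1: "In total we hope to recruit between 3-6 GP sites across Leicestershire and Northamptonshire for the study".
- Section 11.2: "We plan to recruit 1000 children into the study".
- Section 11.3: "All statistical tests will be performed at the alpha=5% level", with no mention of one- or two-sided testing.

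**The concern.** Objectives 1 and 2 ask how many children's diagnoses are supported or overturned by objective testing. The natural answer is a pair of proportions with intervals. The plan offers rank tests instead, which raises two problems.

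First, a misdiagnosis in the sense of section 5.2 exists only once the tests have been done. A before-after test of it has nothing on the before side.

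Second, a change in the number diagnosed is a net figure. A child who loses the label and a child who gains it cancel. The study population makes movement in both directions likely: section 7.2 admits children on the asthma register and also children found only through prescriptions or an exacerbation.

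At stake is whether these two objectives are answered by a p-value that does not measure diagnostic error, with no interval estimate specified for either.

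**Working it through.** **The plan's own figure.** The 1000 in section 11.2 is a feasibility count: 1500–2000 eligible × 50–70% response = 750 to 1400, which contains 1000 (2000 × 50% = 1000). No power calculation or expected rate of diagnosis change is given, so the counts of changed diagnoses below are assumptions.

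**Child as unit.** Let b be diagnoses removed and c diagnoses added, with m = b + c. Every non-zero difference is ±1, so all m differences share the mid-rank (m + 1)/2. Then:
- signed-rank sum minus its mean = (c − b)(m + 1)/4
- tie-corrected variance = m(m + 1)²/16
- z² = (b − c)²/(b + c), which is McNemar's chi-square without continuity correction.

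Numerical checks: 120 v 80 gives 40²/200 = 8.0 (p = 0.0047) for signed-rank, tie-corrected two-period Friedman and McNemar alike. For 130 v 100, signed-rank and McNemar both give 30²/230 = 3.913.

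**Masking.** Section 4 reports, from a small sample, that the total identified was about 4 times the number on the register. Take that as roughly 1000/4 = 250 children diagnosed before and 750 not.
- Suppose 30% of the 250 lose the diagnosis (the upper figure section 4 gives, for adults) and 10% of the 750 gain one (assumed). Then b = 75 and c = 75, net change is 0, and (75 − 75)²/150 = 0, so p = 1.0. Yet (75 + 75)/1000 = 15% were reclassified.
- Suppose instead that 20% change in each group: b = 50, c = 150, and (100)²/200 = 50. This is overwhelmingly significant, yet the rates of change are equal and the result reflects only the sizes of the two groups.

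Separate proportions do not have this fault. In the first case, removed = 75/250 = 30%, SE = √(0.30 × 0.70/250) = 0.029, 95% CI 24.3% to 35.7%. Newly diagnosed = 75/750 = 10%, SE = √(0.10 × 0.90/750) = 0.011, 95% CI 7.9% to 12.1%. These simple intervals ignore clinic and would probably widen once it is allowed for.

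**Practice as unit (only if so chosen).** Smallest attainable p-values, with all practices moving the same way:

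| Test | 3 sites | 4 | 5 | 6 |
|---|---|---|---|---|
| Exact two-sided signed-rank, or exact two-period Friedman: 2/2ⁿ | 0.25 | 0.125 | 0.0625 | 0.031 |
| Exact one-sided signed-rank: 1/2ⁿ | 0.125 | 0.0625 | 0.031 | 0.016 |
| Asymptotic signed-rank, uncorrected | 0.109 | 0.068 | 0.043 | 0.028 |
| Asymptotic two-period Friedman: chi-square = n, 1 df | 0.083 | 0.0455 | 0.025 | 0.014 |

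**Misdiagnosis.** No arithmetic applies. Under section 5.2 the value before testing is absent by definition, so neither the signed-rank nor the Friedman test has a pair to work on.

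**The case against.** Four points can fairly be made for the plan.

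1. The tests are introduced only as examples, and the logit mixed model may be meant to cover these outcomes, since the synopsis counts them among the secondary outcomes. This stands as far as it goes: there is room for a sound analysis. But the model names neither diagnosis outcome, and nothing specifies an estimate with an interval in each direction.
2. A reader might infer that the named tests are invalid for these data. The documents do not support that. On paired 0/1 data per child two of them reproduce McNemar's test, so they are unusual labels for a standard test, apart from ignoring clinic. Nor does section 11.1 assign Kruskal-Wallis to before-after data.
3. A reader might infer that the tests cannot reach 5% with the planned number of practices. That does not follow either. Section 11.1 does not make the practice the unit, and recruitment and record review are per child. Even at practice level the limit applies to exact two-sided paired tests with 3–5 sites. Some asymptotic or one-sided versions can pass 5%, though the approximations are unreliable at such numbers, and 6 sites is within plan.
4. The sentence in 11.1 can be read so that change refers to diagnoses alone, and misdiagnoses are a separate objective, so movement need not be reported only as one net figure. This is fair. On that reading, though, the paired tests have no role for misdiagnoses, and Kruskal-Wallis across practices would compare practices without estimating how many children were misdiagnosed.

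**Conclusion.** The point holds in limited form. Section 11.1 attaches rank tests to two binary child-level outcomes without naming the unit or matching tests to outcomes. A paired test of misdiagnoses is empty, and a test of net change in diagnoses does not measure reclassification. The illustration of 15% reclassified with p = 1.0 rests on assumed counts; the true size depends on how evenly removals and additions balance, which the documents do not give.

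Replacing the named tests with McNemar's would leave the masking untouched; reporting each direction separately removes it. The practice-level floors of 0.25, 0.125 and 0.0625 for 3, 4 and 5 sites matter only if practices are made the unit and exact two-sided paired tests are used. The primary objective, on training and capacity, is unaffected.

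**What to change.** In section 11.1:
- State that the child is the unit of analysis for diagnosis outcomes.
- Report a before-by-after table of recorded asthma diagnosis.
- Give the percentage removed among children diagnosed before and the percentage newly diagnosed among those who were not, each with a 95% confidence interval allowing for GP clinic.
- Report misdiagnoses as a proportion, with its denominator stated and a confidence interval, and with no before-after test.
- For any hypothesis test, name these outcomes under the logit mixed model already planned, or use McNemar's test.
- Do not use Kruskal-Wallis for before-after comparisons.
- Keep signed-rank tests for inhaler counts, steroid courses, asthma control test scores, school days and carer work days.

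The cost is some wording and a little extra analysis. The record review in section 9.1 already collects what is needed, so no new data are required.

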8.2 Screening and Eligibility Assessment

Children who clinically warrant an asthma review, which are also our potential participants, will be identified by the direct care team from participating GP sites. The direct care team will search their practice electronic database for children who meet the inclusion criteria using age limits "5 to 16 years," and to include children who are either on the asthma register or based on asthma medications prescribed as detailed in the inclusion criteria above.

Once identified, the direct care team will send by post the standardised PIS along with the asthma review invitation letters to families. The invitation letter will invite families to phone the GP practice to book onto an asthma review clinic. We anticipate that there will be a minimum of 1 week between the time families receive PIS and the next available asthma review clinic.

Demographics

The date of birth, gender, race, primary language and country of birth will be recorded by the research team in the CRF following written consent at the asthma review.

Medical History

Details of length of asthma diagnosis or duration of “asthma” symptoms will be recorded at time of asthma review by study team following written consent along with concomitant medication and any physical examination (detailed below).

Concomitant Medication

All prescription “asthma” medications (bronchodilators, inhaled steroids, leukotriene receptor antagonists etc.) will be recorded on CRFs and assigned to a corresponding asthma treatment step as detailed in BTS/SIGN asthma guidelines. We will also record number of days of oral steroids prescribed in the preceding 6 months.

Physical Examination

Height and weight of participating children will be recorded.

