8.3 Baseline Assessments

Health Care Workers’ Training Needs

The study team will gather information using site survey and readiness for change questionnaires at each participating practice. It is expected that practice GPs, nurses, HCAs and managers will complete these questionnaires.

The study team will seek the views particularly, but not exclusively, of the healthcare workers performing the objective tests (spirometry and FeNO) on the delivery and content of the training package and the training time available to those performing the tests.

Assessments Performed as Part of Recommended Standard Asthma Review

Asthma control test: We will use validated asthma control tests for children 4 to 11 years (7 questions) (17) and children 12 years and older (5 questions).

Check inhaler technique: Inhaler technique will be checked by the PN/HCA following training if required. An instruction sheet with written information and pictures will be given to the family.

Check prescription record: We will check and document the electronic prescribing record and dispensing record where available for asthma medication in the previous 6 months including the number of reliever and preventer inhalers. As part of the asthma review the practice PN/HCA will also check the prescription records and inform the GP if they have concerns regarding: suboptimal asthma control; where reliever and preventer medication use are unbalanced for example in cases where preventer prescribing is low and reliever prescriptions are high; and where there are concerns regarding adherence (i.e. fewer than expected number of inhalers dispensed).

Any child presenting to the review visit unwell or with poor lung function (FEV1 <75% predicted) will be referred to the practice GP for assessment.

Written personalised asthma action plan: All children will be given a written personalised asthma action plan. Where children already have an action plan this will be reviewed.

Spirometry and FeNO testing: Children will be asked to perform spirometry and a FeNO measurement where indicated.

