8.5 Subsequent Assessments

We will have only one face to face contact with each study participant throughout the study. Having taken appropriate consent, we will review each participants electronic record 3-6 months following the initial asthma review to record any changes in prescription patterns, additional primary care review for exacerbations or hospital attendances. In patients who have agreed, we will also send out a follow up postal health economic questionnaire and asthma control test 3-6 months following the review.

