8.6 Definition of End of Trial

The end of trial is when the last participant has attended his/her asthma review clinic and we have reviewed his/her records 3-6 months following this date.

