8.8 Source Data

Source documents are original documents, data, and records from which participants' CRF data are obtained. These include, but are not limited to, GP electronic records (from which medical history and previous and concurrent medication may be summarised into the CRF) and hospital correspondence.

CRF entries will be considered source data if the CRF is the site of the original

recording (e.g., there is no other written or electronic record of data). In this study the CRF will be used as the source document for time taken to perform spirometry and FeNO and health economic questionnaire answers only.

All documents will be stored safely in confidential conditions. On all study-specific documents, other than the signed consent, the participant will be referred to by the study participant number/code, not by name.

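### Prescribing before the asthma review is recorded over a fixed 6 months, but no rule sets the window after it; if only items issued since the review are counted, the comparison leans towards a fall.

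*Combined protocol and SAP*

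**What the plan says.** Before the review, section 8.3 documents "asthma medication in the previous 6 months including the number of reliever and preventer inhalers". For oral steroids, section 8.2 says: "We will also record number of days of oral steroids prescribed in the preceding 6 months". Section 8.2 also has each child's medication "assigned to a corresponding asthma treatment step as detailed in BTS/SIGN asthma guidelines".

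After the review there is one look at the record. Section 8.5 says: "we will review each participants electronic record 3-6 months following the initial asthma review to record any changes in prescription patterns". The end-of-trial definition in 8.6 repeats the range: "we have reviewed his/her records 3-6 months following this date". Section 9.1, on processes of care, lists the information sought as "changes to prescribed asthma medications (bronchodilators, oral steroids and inhaled steroids), exacerbations since review, hospital admissions/attendances since review".

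Section 11.1 then tests "alterations in prescribing (number of salbutamol inhalers/steroid courses) as a result of implementation of objective lung function tests" with non-parametric methods, giving Kruskal-Wallis, the paired Wilcoxon test and Friedman's test as examples. It also names a logit-link mixed model for proportions, and a mixed effects model with GP clinic as a random effect for which neither link nor outcome is given.

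**The concern.** A before-after comparison of counts needs equal observation time on both sides, or an analysis that allows for unequal time. Here the pre-review period is 6 months. The post-review period is undefined, and at most 6 months of it can have elapsed when the record is read. Nothing in 8.5, 9.1, 11.1, 11.5 (missing data) or 11.7 (inclusion in analysis) sets a look-back, a common cut-off or a rate.

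If items are counted from the review to the check, most children have less time to collect prescriptions afterwards than before. Any error then runs one way, towards fewer reliever inhalers and steroid courses, which is the result that would favour implementation. A larger sample makes a false finding more likely. A real rise could be hidden or reported as a fall.

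**Working it through.** **Inputs from the documents.** Baseline window 6 months (8.2, 8.3); check at T = 3 to 6 months (8.5, 8.6); planned n = 1000 (11.2); alpha 5%, sidedness not stated (11.3), taken as two-sided.

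**The plan's own figure.** None is given for prescribing. The 1000 is a feasibility count: 1500-2000 eligible children (6.1) x 50-70% recruitment gives 1500 x 0.50 = 750 to 2000 x 0.70 = 1400, and 2000 x 0.50 = 1000. No power calculation is involved.

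**Reading (a): items since the review.** At a constant rate, expected follow-up/baseline = T/6.

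- All checks at 3 months: 3/6 = 0.50
- Checks even over 3-6 months (mean 4.5): 4.5/6 = 0.75
- Checks even over 4.5-6 months (mean 5.25): 5.25/6 = 0.875
- Checks even over 5-6 months (mean 5.5): 5.5/6 = 0.92
- All checks at 6 months: 6/6 = 1.00

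The ratio is never above 1.

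To see what the paired Wilcoxon test does with this, counts were simulated with no true change. These assumptions are not in the documents: each child's 6-month rate follows a gamma distribution with mean 0.1 or 0.2 (steroid-like) or 0.5, 1 or 2 (salbutamol-like) and shape 0.5, 1 or 2; baseline is Poisson(rate); follow-up is Poisson(rate x T/6). Zeros were dropped and ties corrected, with 2000 trials per cell. The table gives the percentage of trials declaring a false fall; ranges span the shapes.

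| Mean items per 6 months | 0.1 | 0.2 | 0.5 | 1 | 2 |
|---|---|---|---|---|---|
| n=1000, checks over 3-6 months | 44-46 | 75-77 | 98-99 | 100 | 100 |
| n=1000, over 4.5-6 months | 14-15 | 24-27 | 51-52 | 79-82 | 97-98 |
| n=1000, over 5-6 months | 8 | 13 | 26 | 44-45 | 73-75 |
| n=500, over 3-6 months | 26-27 | 47-48 | 82-83 | 98-99 | 100 |
| n=500, over 5-6 months | 6-7 | 8-9 | 14-16 | 25-26 | 44 |

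With all checks at 6 months, total rejection is 5-6%.

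For a true 20% rise with checks over 3-6 months, 1.2 x 0.75 = 0.90, so the rise reads as a 10% fall. At n=1000 (shape 1) a fall is declared in 10%, 18%, 36%, 61% and 88% of trials across the five means, and the rise is detected in under 1%. Matched windows detect it in 21%, 36%, 73%, 95% and 100%.

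**Reading (b): 6-month look-back from the check.** The follow-up window then includes the last 6 - T months before the review, up to (6 - 3)/6 = half of it. Those items appear in both counts and cancel in the paired difference. Rejection with no change stays about 5%, and power for a 20% rise at mean 0.5 is 73%, as with matched windows. The size of the change is diluted: with checks even over 3-6 months the mean pre-review share is (6 - 4.5)/6 = 25%, so a 20% rise reads as about 1 + 0.2 x 0.75 = 1.15, or 15%.

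**Steroid unit.** Section 8.2 collects days; 11.1 analyses courses. No section collects baseline courses over any window.

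**The case against.** The strongest reply is that the bias depends on reading (a), which the plan does not state for medication. A reader might infer it from the causal wording of 11.1, since only post-review items can show an effect of testing, and from 9.1. But 9.1 ties exacerbations and hospital contacts to the time since the review and does not do so for medication; that contrast can be read either way. On reading (b) the test keeps its size. This stands: the missing window is a fact, the false fall is conditional.

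Four further points also stand in part.

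- Section 11.1 does not say that the 6-month records in 8.2 and 8.3 are its comparator, though they are the only dated baseline prescribing windows given. For steroid courses, the mismatch is inferred from a record of days.
- Section 11.1 offers its tests as examples, so another could be chosen. That does not define what is being counted.
- The simulated sizes assume single items issued independently. If inhalers are issued in pairs (assumed), the false fall at mean 1 with checks over 5-6 months drops from about 45% to 24%.
- A reader might infer that the data are lost unless the window is fixed before extraction. They are not: the follow-up check reopens the same GP record, which 8.8 names as a source, and a matched pre-review count can be taken then.

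**Conclusion.** The concern holds in conditional form. Confidence is high that no post-review prescribing window or time adjustment is set, and moderate that the bias would occur. If only items since the review are counted, the expected ratio under no change is 0.50-1.00. At n=1000 a false fall is then declared in about 45-100% of trials with checks even over 3-6 months and about 8-75% over 5-6 months, under the assumed rates and check dates. If all checks are at 6 months there is no window bias. On a 6-month look-back, only the reported size of change suffers.

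Two stronger conclusions are not supported. The first is that the study's main result is at risk: this is a process-of-care outcome (9.1, 11.1), neither the primary endpoint (6.2) nor a numbered secondary objective (5.2), and comparing treatment steps needs no window. The second is that equal windows alone would make the salbutamol test valid. They restore about 5% rejection only for children not selected on prescribing. Inclusion criteria 3 and 4 (7.2) select on two or more salbutamol inhalers, or an exacerbation, in the last 12 months, so regression to the mean remains. If 25% of children entered through criterion 3 (an assumed share) and the rest were unselected, matched windows with no true change would still give a false fall in about 86-88%, 34% and 11-12% of trials at means 0.5, 1 and 2 (n=1000, shape 1, checks over 3-6 months). The true size cannot be worked out from the documents.

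**What to change.** 1. In 8.5, count prescriptions issued after the review and record each child's check date.
2. In 11.1, compare that count with the same length of time immediately before that child's review, using the paired Wilcoxon test. Alternatively, use a count model with a log(months observed) offset, a child-level term and child-clustered robust standard errors. Without selection on prescribing, matched windows reject in 4-6% of simulated trials with no change. If a child's rate also varies between periods (assumed gamma shape 2), model-based errors reject in 6-23% at n=1000 and robust errors in 4-5%.
3. Do not divide counts by months and then apply the Wilcoxon test, at any prescribing rate. With no change and n=1000, this declares a false rise in about 60% and 49% of trials at means 0.1 and 0.2 with checks over 3-6 months, and in about 90%, 66-69% and 27-30% at means 0.5, 1 and 2 with checks over 5-6 months.
4. Record steroids in one unit, courses or days, in both periods.
5. Because regression to the mean remains and there is no control group, report the result as change after the review, not as caused by testing.

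**Cost.** Wording in 8.5 and 11.1, the check date, and dated items or a matched pre-review count taken at the planned check. No extra follow-up is needed. Matching discards 0-50% of the baseline window: on average 25% with checks even over 3-6 months and 8% over 5-6 months. Power for a true 20% rise at n=1000, matched Wilcoxon against robust offset model, is 21% v 23%, 36% v 40%, 73% v about 79% and 95% v 98% at means 0.1, 0.2, 0.5 and 1. The offset model costs only analysis work.
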